#### **6.2.1.1 Formulation**

Details of the NrtI formulations are specified in the respective package inserts.

#### **6.2.1.2 Packaging and Labeling**

Details of the NrtI packaging and labeling are specified in the respective package inserts.

#### **6.2.1.3 Dosage and Administration**

Details for the NrtI dosage and administration are specified in the respective package inserts. The NrtI should be taken with VBR at approximately the same time each day.

#### **6.2.1.4 Storage and Handling**

Details for the NrtI storage and handling are specified in the respective package inserts.

### **6.2.2 Accountability for NIMPs**

Oversight of background medication (NrtI) according to product label will be provided by the Investigator. Dose administration of NIMPs will be recorded in the subject diary.

## **6.3 Concomitant Medications**

A concomitant medication is defined as any prescription or over-the-counter preparation, including vitamins, medications, vaccinations, herbal preparations and supplements that is taken by a subject during the conduct of the clinical trial.

All concomitant medications taken from the date the informed consent is signed through end of study or “lost to follow-up” must be recorded in the subject’s source documentation. This information should include the name of the medication, the dosage, the start and stop dates, and the indication for which the concomitant medication was administered.

### 6.3.1 Prohibited Concomitant Therapy

Concomitant use of certain medications or herbal/natural supplements (inhibitors or inducers of drug transporters [ie, P-glycoprotein] or metabolizing enzymes [ie, cytochrome P450s]) may result in PK interactions that increase or decrease the exposure of VBR or the concomitant medication. Examples of representative medications which are prohibited from 28 days prior to Day 1 through 2 weeks after the last dose of VBR or “lost to follow-up” are listed in [Table 8](#). Investigational agents are also prohibited. Provisions regarding concomitant medications described in the respective NrtI package inserts must also be followed during the study through the end of the follow-up period.

Medications with narrow therapeutic indices should be avoided or used with caution (representative medications are shown in [Table 8](#)). Narrow therapeutic drugs that are substrates for CYP2C9 are prohibited.

Should subjects need treatment with any prohibited concomitant medication, the Medical Monitor must be consulted prior to initiation of the new medication. In instances where a prohibited concomitant medication is initiated prior to discussion with the Medical Monitor, the Investigator must notify the Sponsor as soon as he/she is aware.

Note that systemic (oral, injectable, or implanted) hormonal contraceptives are not considered as an acceptable means of contraception for female subjects of child-bearing potential ([Appendix 2](#)) up to 28 days after the last dose of VBR (Groups 1 and 2 in [Figure 6](#)). For AB-729, the use of hormonal contraceptives is acceptable for female subjects of child-bearing potential as long as they use a second non-hormonal form of contraception during the study and up to 6 months after the last dose of AB-729 (Group 3 in [Figure 6](#)).

**Table 8. Prohibited Concomitant Therapies**

Drug Class	Prohibited Medications	Use with Caution
Antiarrhythmics		Quinidine
Anticonvulsants	Phenytoin, carbamazepine, phenobarbital, oxcarbazepine	Digoxin
Antidepressants		Amitriptyline, doxepin, fluoxetine, venlafaxine
Antimycobacterials	Rifamycins	
Cardiac Medications	Warfarin, digoxin	Irbesartan, losartan
Hypoglycemics	Troglitazone	Glimepiride, glipizide, glyburide, nateglinide, rosiglitazone, tolbutamide, chlorpropamide, nateglinide
Herbal/Natural Supplements	St. John’s Wort, echinacea, milk thistle, grapefruit/grapefruit juice	

Drug Class	Prohibited Medications	Use with Caution
Nonsteroidal anti-inflammatory drugs (NSAIDs)		Celecoxib, diclofenac, ibuprofen, lornoxicam, meloxicam, naproxen, piroxicam, suprofen
Others	Barbiturates, modafinil	

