  - e. Serum alpha fetoprotein (AFP)  $\geq 100 \text{ ng/mL}$ . If AFP at Screening is  $> \text{ULN}$  but  $<100 \text{ ng/mL}$ , the subject is eligible if hepatic imaging prior to initiation of study drug reveals no lesions indicative of possible HCC
  - f. INR  $>1.5 \times \text{ULN}$
  - g. Estimated creatinine clearance (CrCl)  $<50 \text{ mL/min}$  (using the Cockcroft-Gault method) based on serum creatinine and actual body weight at Screening
  - h. Any other laboratory abnormality deemed clinically significant by the Investigator
12. Current or prior use of prohibited concomitant medications from 28 days prior to Day 1 ([Section 6.3.1](#))
13. Current or prior treatment for cHBV with:
  - Lamivudine, telbivudine or adefovir (any duration)
  - HBV core inhibitor (any duration)
  - siRNA or other oligonucleotide therapeutic (any duration)
  - Interferon in the 6 months prior to Screening

- Any investigational agent for cHBV in the 6 months prior to Screening

14. Participation in another clinical study of a drug or device whereby the last investigational drug/device administration is within 60 days or 5 half-lives prior to the first study drug administration, whichever is longer

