### 10.3 Analysis Populations

The following populations will be considered for analysis of various endpoints:

- **Randomized Analysis Set:** It includes all randomized subjects who satisfied the inclusion and exclusion criteria described in this protocol.
- **Full Analysis Set:** It includes all randomized subjects, classified according to the treatment group into which they were randomized regardless of the actual treatment received, who took at least 1 dose of study drug. It is the main analysis population for the efficacy analysis.
- **Safety Analysis Set:** It includes all subjects, classified according to the actual treatment received regardless of random assignment, who took at least 1 dose of study drug. This is the main analysis population for all safety analyses.
- **Pharmacokinetic-Evaluable Set:** It consists of all subjects, classified according to the actual treatment received regardless of random assignment, who receive at least 1 dose of study drug. At least 1 pharmacokinetic blood sample following a dose of study treatment is required for inclusion in this analysis. This is the main analysis population for all pharmacokinetic analyses.

Based on the actual deviations, the criteria for exclusion of subjects from the different data sets will be specified and updated, if necessary, prior to database lock.

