### 4.3. Protocol Deviations

Subjects who did not meet the eligibility criteria for study entry but enrolled in the study will be summarized. The number and percentage of subjects who did not meet at least 1 eligibility criterion will be provided for specific criteria by treatment group based on the All Randomized Analysis Set. A by-subject listing will be provided for those subjects who did not meet at least 1 eligibility (inclusion or exclusion) criterion. The listing will present the eligibility criterion (or criteria if more than 1 deviation) that subjects did not meet and related comments, if collected.

Protocol deviations (PDs) occurring after subjects entered the study are documented during routine monitoring. The number and percentage of subjects with important PDs (IPDs) by deviation category will be summarized by treatment group for All Randomized Analysis Set. A table will be provided to summarize any COVID-19 related PDs with the deviation reason by treatment groups. A by-subject listing will be provided for those subjects with any protocol deviations.

A table will be provided to summarize any COVID-19 related PDs with the deviation reason by treatment groups. Any visits that were not performed will be summarized by reason (ie, adverse event, COVID-19 restrictions, and Other). A listing of subjects who had study disruption due to COVID-19 will be provided with a description.

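### Protocol Table 8 lists digoxin both as prohibited and as usable with caution, and nothing says which entry governs

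*Combined protocol and SAP*

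**What the plan says.** Protocol Table 8 has one column for prohibited drugs and one for drugs to be used cautiously. Digoxin is in both: the prohibited cell of the cardiac row reads "Warfarin, digoxin", and digoxin stands alone in the caution cell of the anticonvulsants row.

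Section 6.3.1 introduces the prohibited entries as "Examples of representative medications which are prohibited from 28 days prior to Day 1 through 2 weeks after the last dose of VBR". If a subject needs a prohibited drug, "the Medical Monitor must be consulted prior to initiation of the new medication", and the Sponsor must be told if the drug was started before that discussion. On narrow-index drugs the section says "Medications with narrow therapeutic indices should be avoided or used with caution", refers to the same table for examples, and adds: "Narrow therapeutic drugs that are substrates for CYP2C9 are prohibited".

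Exclusion criterion 12 (Section 5.3, repeated in the Synopsis) bars "Current or prior use of prohibited concomitant medications from 28 days prior to Day 1" and cites Section 6.3.1.

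**The concern.** A site that looks up digoxin finds two instructions, and Table 8 is the list that the eligibility criterion and the co-medication rules rely on. The list exists because some co-medications may change exposure to vebicorvir or to the other drug. The trial's primary objective is safety and about 25 sites are planned. Contradictory entries could lead to uneven screening decisions, uneven handling of a drug started on study, and the same event being recorded as a deviation at one site and not at another.

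**Working it through.** No formula applies and the plan states no figure on this point. The check compares the table with the text that depends on it.

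1. **Could PDF reading have produced the conflict?** Digoxin sits oddly beside anticonvulsants, so a row shift is possible. A row shift changes the row and leaves the column as it was: moved up to the antiarrhythmics row beside quinidine, digoxin would still be under caution. Both columns are filled in the two affected rows, and a shift would not create a second entry. The same table repeats nateglinide within one cell, which points to an authoring slip.

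2. **Does other text settle it?** Section 6.3.1 bans narrow-index drugs that are CYP2C9 substrates, but neither document says whether digoxin is one. The sentence on avoidance or caution is compatible with either column. Calling the table entries representative examples does not help with a drug that is named. Exclusion 12 does not name digoxin; it relies on Section 6.3.1, which relies on Table 8.

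3. **What differs between the two readings?**

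| Matter | Prohibited entry governs | Caution entry governs |
|---|---|---|
| Use within 28 days before Day 1 | Excluded by criterion 12; Section 8.3 allows no waivers | Criterion 12 does not apply |
| Start on study, up to 2 weeks after last vebicorvir dose | Medical Monitor consulted first; Sponsor told if not | No such step stated |
| Reporting | Can count as an eligibility failure or deviation | Does not count on this ground |

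4. **Which analyses could move?** Protocol Section 10.3 defines its Randomized Analysis Set by eligibility: "It includes all randomized subjects who satisfied the inclusion and exclusion criteria described in this protocol". The SAP does not keep that condition. Its All Randomized Analysis Set (3.1.1) takes every randomized subject, and its Full and Safety Analysis Sets (3.1.2, 3.1.3) turn on at least one dose of study drug. What remains is SAP Section 4.3: "Subjects who did not meet the eligibility criteria for study entry but enrolled in the study will be summarized", with counts and percentages by treatment group, and the summary of important deviations.

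5. **Size for one subject.** With the planned group sizes of 30, 15 and 15, reclassifying one subject changes an eligibility-failure percentage by 1/30 = 3.3 points in Group 1, or 1/15 = 6.7 points in Group 2 or 3. This is an illustration; the documents report no such subject.

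**The case against.** The strongest reply is that this is an editing slip with almost nobody exposed to it. Subjects are 18 to 50 and must be generally well apart from hepatitis B. Exclusion 5 covers significant cardiac disease and exclusion 8 covers significant ECG abnormalities. A site that noticed both entries could query them before acting. The SAP also records that the study was stopped after every active subject had completed the 48-week treatment period, so a correction can no longer change on-treatment handling. Most of this stands, and it keeps the severity low. It does not remove the contradiction: exclusions 5 and 8 rest on judgement and are not an absolute bar to digoxin use, and no text gives one entry precedence.

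A reader might also infer more than the documents support:

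- **That two sites would decide oppositely.** They could; nothing shows that they would or did.
- **That the protocol contradicts itself on a drug it calls narrow-index.** It never gives digoxin that label by name. The label is at most implied by the reference to Table 8, and the point does not need it.
- **That Section 6.3.1 and exclusion 12 are themselves faulty.** Neither names digoxin; they inherit the ambiguity.
- **That the analysis populations are compromised.** Only the protocol's eligibility-based set could be touched, and the SAP replaces it.

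**Conclusion.** The table is wrong as written: an internal inconsistency of low severity. One drug has two incompatible entries in a list that drives an exclusion criterion and on-study co-medication rules. Few subjects, if any, are likely to be affected, and the statistical reach is confined to eligibility and deviation summaries. No sample-size figure, efficacy estimate or SAP analysis set depends on it.

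This rests on two assumptions: that the extracted text keeps the table's columns correctly, which the filled cells in both rows support, and that no site guidance outside the protocol and SAP already settled the matter.

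**What to change.** Reconcile the two digoxin entries in Table 8 so that the drug appears in one column only. Which column is a clinical decision for the sponsor, and this review takes no position on it. Section 6.3.1 and exclusion criterion 12 need no separate change because they take their content from the table by reference.

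The cost is one table correction. With the treatment period over, its use is in classifying any recorded digoxin use the same way across sites in the deviation summaries, and in any later protocol that reuses this table.

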## **6.4 Randomization, Blinding, and Treatment Codes**

### **6.4.1 Randomization**

All subjects will be assigned a unique Subject identification (ID) at Screening and will be randomized upon successful completion of the Screening assessments. Upon confirmation of subject eligibility on Day 1, an Interactive Response Technology (IRT) system will assign eligible subjects to a study treatment, as shown in [Table 7](#). Additional information on the use of the IRT system is provided in the IRT User Manual.

### **6.4.2 Blinding**

This is an open-label study.

## 7 DISCONTINUATION OF STUDY TREATMENT AND SUBJECT DISCONTINUATION/WITHDRAWAL

### 7.1 Discontinuation of Study Treatment

With the exception of treatment cessation based on Treatment Stopping Criteria (see [Section 4.1.1](#)), if an individual subject is not satisfactorily tolerating their assigned treatment due to any AEs in the judgment of the Investigator, then, upon consultation with the Sponsor, the Investigator may discontinue treatment with VBR and/or AB-729 depending on the treatment group assignment. Discontinuation from treatment does not mean discontinuation from the study. Subjects who prematurely discontinue their assigned treatment regimen should immediately undergo the assessments listed for the Premature Termination visit ([Section 8.5](#)) and then continue scheduled follow-up assessments ([Table 11](#)).

- If both or either IMP is discontinued, the subject may remain on NrtI as clinically indicated at the discretion of the Investigator.
- For subjects in Group 1, if the NrtI is discontinued, then VBR must also be discontinued; treatment with AB-729 may be continued following discussion with the Medical Monitor. In this event, subjects will not be required to undergo a premature termination visit, and will continue with their scheduled visits, as planned.

### 7.2 Criteria for Discontinuation of Study Treatment

With the exception of treatment cessation based on Treatment Stopping Criteria (see [Section 4.1.1](#)), study drug treatment may be discontinued in the following instances:

- Intercurrent illness that would, in the judgement of the Investigator, affect assessments of clinical status to a significant degree
- Unacceptable toxicity as defined in [Section 9.10](#) (Toxicity Management), or toxicity that, in the judgment of the Investigator, compromises the ability to continue study-specific procedures or is considered to not be in the subject's best interest
- Lack of efficacy (virologic failure)
- Subject noncompliance
- Pregnancy during the study
- Discontinuation of the study at the request of the Sponsor, a regulatory agency or an Institutional Review Board or Independent Ethics Committee (IRB/IEC)

### **7.3 Subject Discontinuation/Withdrawal from the Study**

A subject may withdraw from the study at any time at his/her own request or may be withdrawn at any time at the discretion of the Investigator or Sponsor for safety, behavioral, compliance, or administrative reasons. This is expected to be uncommon. At the time of discontinuing from the study, if possible, a Premature Termination visit should be conducted ([Section 8.5](#)).

#### **7.3.1 Subject Lost to Follow-Up**

A subject will be considered lost to follow-up if they repeatedly fail to return for scheduled visits and is unable to be contacted by the study site. The following actions must be taken if a subject fails to return to the clinic for a required study visit:

- The site must attempt to contact the subject, reschedule the missed visit as soon as possible, and counsel the subject on the importance of maintaining the assigned visit schedule and ascertain whether or not the subject wishes to and/or should continue in the study.
- Before a subject is deemed lost to follow-up, the Investigator or designee must make every effort to regain contact with the subject (where possible, 3 telephone calls and, if necessary, a certified letter to the subject's last known mailing address or local equivalent methods). These contact attempts should be documented in the subject's medical record.

Should the subject continue to be unreachable, they will be considered lost to follow-up.

## **8 STUDY PROCEDURES AND ASSESSMENTS**

### **8.1 Schedule of Assessments**

All procedures for Cohort 1 of this study are outlined in [Table 9](#).

**Table 9. Schedule of Assessments (Cohort 1) – On-Treatment for All Subjects**

Period or Visit	Screen	On Treatment														PT a	UV b
Study Day or Week	D-45 to D-1	D 1	Wk 2	Wk 4	Wk 8	Wk 12	Wk 16	Wk 20	Wk 24	Wk 28	Wk 32	Wk 36	Wk 40	Wk 44	Wk 48	NA	NA
Visit Windows (days)	NA	0	±3	±3	±3	±3	±3	±3	±3	±3	±3	±3	±3	±3	±3	NA	NA
Informed Consent(s)	X																
Demographics, medical history & HBV history	X	X															
Height	X																
Weight	X	X							X						X		
Vital signs	X	X	X	X	X	X	X	X	X	X	X	X	X	X	X	X	X
Complete physical exam	X	X							X						X	X	
Symptom-directed physical exam			X	X	X	X	X	X		X	X	X	X	X			X
12-lead ECGc	X	X				X			X			X			X	X	
Review of concomitant medications & AEs	X	X	X	X	X	X	X	X	X	X	X	X	X	X	X	X	X
Liver staging	X d																
Fibroscan® (if available)	X								X						X	X	
FibroTest®, APRI	X								X						X	X	
Chemistry, hematology, coagulation	X	X	X	X	X	X	X	X	X	X	X	X	X	X	X	X	X
CrCl	X	X							X						X	X	X
AFP, HbA1c	X																
Pregnancy teste	X	X	X	X	X	X	X	X	X	X	X	X	X	X	X	X	X
Urinalysis		X	X	X	X	X	X	X	X	X	X	X	X	X	X	X	X
Urine drug test	X																
HBV genotype	X f																
HBV DNA (COBAS® TaqMan®)	X	X				X			X			X			X	X	X
HBV RNA (COBAS®)	X	X	X	X	X	X	X	X	X	X	X	X	X	X	X	X	X
HBV TNA	X	X	X	X	X	X	X	X	X	X	X	X	X	X	X	X	X
Qualitative HBeAg	X	X													X	X	
HBeAb	X	X													X	X	
Quantitative HBsAgg	X	X	X	X	X	X	X	X	X	X	X	X	X	X	X	X	X
HBsAbg	X	X													X		
HBcrAg	X	X													X	X	

Vebicorvir  
 ABI-H0731-204 Protocol Amendment 1 27 October 2021

Period or Visit	Screen	On Treatment														PT a	UV b
Study Day or Week	D-45 to D-1	D 1	Wk 2	Wk 4	Wk 8	Wk 12	Wk 16	Wk 20	Wk 24	Wk 28	Wk 32	Wk 36	Wk 40	Wk 44	Wk 48	NA	NA
Visit Windows (days)	NA	0	±3	±3	±3	±3	±3	±3	±3	±3	±3	±3	±3	±3	±3	NA	NA
HBsAg isoforms and immune complexes	X	X	X	X	X	X	X	X	X	X	X	X	X	X	X	X	X
Sample for HBV resistance monitoring	X	X	X	X	X	X	X	X	X	X	X	X	X	X	X	X	X
Virology back-up sample h	X	X	X	X	X	X	X	X	X	X	X	X	X	X	X	X	X
Immune biomarkers/cytokines		X	X	X	X	X		X		X		X		X		X	X
PBMCs i		X	X	X	X	X		X		X		X		X		X	X
RNAi biomarker sample		X	X	X	X	X	X	X	X	X	X	X	X	X	X	X	X
HCV Ab, HDV Ab, HIV Ab, HAV Ab, HEV Ab	X																
Confirm subject eligibility	X	X															
Randomization		X															
Dispense VBR		X		X	X	X	X	X	X	X	X	X	X	X			
VBR administration (Groups 1, 2)		X	X	X	X	X	X	X	X	X	X	X	X	X	X		
NrtI administration (All subjects)		X	X	X	X	X	X	X	X	X	X	X	X	X	X		
AB-729 administration (Group 1, 3)		X			X		X		X		X		X				
VBR accountability			X	X	X	X	X	X	X	X	X	X	X	X	X	X	X
Review subject dosing diary			X	X	X	X	X	X	X	X	X	X	X	X	X	X	X
Review injection site reaction diary (Groups 1 and 3)			X			X		X		X		X		X		X	
Sparse PK of VBR (Groups 1, 2)		X	X	X	X	X	X	X	X	X	X	X	X	X	X	X	X
Sparse PK of NrtI (All subjects)		X	X	X	X	X	X	X	X	X	X	X	X	X	X	X	X
Sparse PK of AB-729 (Group 1, 3) j		X j			X		X		X		X		X j				
Optional intensive PK substudy of AB-729		X k											X k				
Optional pharmacogenomic sample							X l										

Vebicorvir

ABI-H0731-204 Protocol Amendment 1 27 October 2021

Period or Visit	Screen	On Treatment														PT a	UV b
Study Day or Week	D-45 to D-1	D 1	Wk 2	Wk 4	Wk 8	Wk 12	Wk 16	Wk 20	Wk 24	Wk 28	Wk 32	Wk 36	Wk 40	Wk 44	Wk 48	NA	NA
Visit Windows (days)	NA	0	±3	±3	±3	±3	±3	±3	±3	±3	±3	±3	±3	±3	±3	NA	NA
Assessment of Treatment Stopping Criteria (see Section 4.1.1 )															X m		

Abbreviations: Ab=antibody; AE=adverse event; AFP=alpha fetoprotein; APRI=aspartate aminotransferase to platelet ratio index; CrCl=creatinine clearance; D=day; DNA=deoxyribonucleic acid; ECG=electrocardiogram; HbA1c=glycated hemoglobin; HBcrAg=hepatitis B core-related antigen; HBeAb=anti-hepatitis B e antigen antibody; HBeAg=hepatitis B e antigen; HBsAb=anti-hepatitis B surface antigen antibody; HBsAg=hepatitis B surface antigen; HBV=hepatitis B virus; HCV=hepatitis C virus; HDV=hepatitis D virus; HEV=hepatitis E virus; HIV=human immunodeficiency virus; IRT= Interactive Response Technology; NA=not applicable; NrtI=nucleos(t)ide/reverse transcriptase inhibitor; PK=pharmacokinetic(s); PT=Premature Termination visit; RNA=ribonucleic acid; TNA=total nucleic acids; UV=Unscheduled visit; Wk(s)=week(s); VBR=vebicorvir.

- a Subjects who prematurely discontinue their assigned treatment regimen before the Week 48 visit should immediately undergo the assessments listed for the Premature Termination visit and then continue with Weeks 52 to 96 follow-up assessments (see [Table 11](#)).
- b Any subject with ALT elevation as defined in [Section 9.10.4](#) should return to the clinic for an Unscheduled visit.
- c Any clinically significant ECG result will be confirmed.
- d At Screening, liver staging will be done EITHER via FibroScan® (if available)/ other Sponsor-approved hepatic imaging method OR via liver biopsy.
- e A serum pregnancy test is required at Screening for female subjects of child-bearing potential. On Day 1, both urine and serum will be performed (subjects may begin treatment based on urine results; any subjects negative by urine subsequently found to be positive on serum should immediately discontinue treatment). All post-Day 1 pregnancy tests may be conducted by urine dipstick. If positive on dipstick, reflex to serum.
- f HBV genotype samples will be collected and stored for analysis by sequence methodology.
- g Quantitative HBsAg assay will be performed at Screening and all study visits. If quantitative HBsAg is <LLOQ, then reflex to qualitative HBsAg. HBsAb is performed at Screening, Day 1, and Week 48. Additionally, if HBsAg is <LLOQ then reflex testing of HBsAb will also be performed.
- h The virology back-up sample will be used for retesting the specified HBV parameters.
- i PBMC collection at selected sites only; not to be collected at subsequent timepoints if not collected at Day 1.
- j A sparse PK sample will be collected for AB-729 at 2 hours (±1 hour) postdose at Weeks 8, 16, 24, and 32 visits. At Day 1 and Week 40, a sparse PK sample will be collected at 2 hours (±1 hour) postdose from subjects who do not participate in the intensive PK substudy.
- k Optional intensive PK substudy of AB-729. Samples will be collected predose, and at 0.5 (±3 min), 1 (±6 min), 2 (±10 min), 4 (±10 min), and 6 (±10 min)- hours postdose (see [Section 8.9.1.2](#)).
- l Pharmacogenomic sample will be obtained only from subjects who provide an additional informed consent. The sample can be collected at a later visit if not collected at Week 16.
- m Subjects will either stop their treatment altogether or continue with NrtI administration based on assessment of Treatment Stopping Criteria ([Section 4.1.1](#)) utilizing laboratory results from the Week 48 Visit. Subjects will remain on assigned oral agents (ie, VBR+NrtI for groups 1 and 2, and NrtI for Group 3) beyond the Week 48 visit until all laboratory results are available to adjudicate the Treatment Stopping Criteria.

